8.3.1 Laboratory Evaluations

Central laboratory will be used for analysis of hematology and clinical chemistry as specified in the visit schedules in [Table 8-1](#) and [Table 8-6](#) . Details on the collections, shipment of the samples and reporting of results by the central laboratory are provided to investigators in the [\[CABL001AUS04 Laboratory Manual\]](#). The time windows granted for laboratory evaluations are identical with the corresponding visit time windows for each visit.

Local laboratory analysis are allowed only if there is a clinical suspicion of abnormal laboratory values which is supported by a reported adverse event.

When abnormal laboratory values or test results constitute an adverse event (i.e. induces clinical signs/symptoms or requires therapy) they must be recorded on the Adverse Events eCRF. Abnormal laboratory values or test results constitute adverse events only if they induce clinical signs or symptoms, are considered clinically significant (e.g. cause study discontinuation or constitutes in and of itself a Serious Adverse Event) or require therapy (e.g., any hematologic abnormality that requires transfusion or cytokine treatment); and should be recorded on the Adverse Events eCRF under the signs, symptoms or diagnosis associated with them. Refer to the visit schedule for the collection frequency.

8.3.1.1 Hematology

Hematology labs are to be analyzed at each scheduled visit by a central laboratory as specified in [Table 8-1](#) and [Table 8-6](#). Hematology includes assessment of hemoglobin, platelets count, red blood cells, total white blood cell count (WBC) and a full manual differential count including basophils, eosinophils, lymphocytes, monocytes, neutrophils, promyelocytes, myelocytes, metamyelocytes, blast and other cells ([Table 8-6](#)).

8.3.1.2 Clinical chemistry

Blood chemistry labs are to be analyzed at each scheduled visits by a central laboratory as specified in [Table 8-1](#) and [Table 8-6](#). Chemistry includes albumin, alkaline phosphatase, ALT (SGPT), AST (SGOT), total calcium, total calcium (corrected for albumin), creatinine, creatinine clearance, creatine kinase, potassium, magnesium, sodium, phosphate (inorganic phosphorus), direct bilirubin, indirect bilirubin, total bilirubin, total cholesterol, LDL cholesterol, HDL cholesterol, total protein, triglycerides, blood urea, Blood Urea Nitrogen (BUN), uric acid, amylase, lipase and fasting glucose.

HbA1c is analyzed at screening/baseline, week 12 and as clinically indicated.

The hepatitis markers HbsAg, HbcAb/anti-Hbc are analyzed at screening/baseline ([Table 8-6](#)).

Table 8-6 Clinical laboratory parameters collection plan

| Test Category | Test Name | Frequency |
|---------------|---|---|
| Hematology | Hemoglobin, platelets, red blood cells, white blood cells, WBC morphology with differential (basophils, eosinophils, lymphocytes, monocytes, neutrophils, promyelocytes, myelocytes, metamyelocytes, blast and other) | Screening/baseline, Week 1 Day 1, Week 2 Day 1, every 4 weeks from week 4 up to Week 72 (EOT) and as clinically indicated |
| Chemistry | Hemoglobin A1c | Screening/baseline, Week 12 and as clinically indicated |
| Chemistry | Creatinine clearance | Screening/baseline |

| Test Category | Test Name | Frequency |
|--------------------------------------|--|---|
| Chemistry | Albumin, alkaline phosphatase, ALT (SGPT), AST (SGOT), total calcium, total calcium (corrected for albumin), creatinine, creatine kinase, potassium, magnesium, sodium, phosphate (inorganic phosphorus), direct bilirubin, indirect bilirubin, total bilirubin, total cholesterol, LDL cholesterol, HDL cholesterol, total protein, triglycerides, blood urea or Blood Urea Nitrogen (BUN), uric acid, amylase, lipase, glucose (fasting) | Screening/baseline, Week 1 Day 1, Week 2 Day 1, every 4 weeks from week 4 up to week 72, (EOT), and as clinically indicated |
| Hepatitis markers | HbsAg, HbcAb /anti-Hbc | Screening/baseline |
| Serum Pregnancy test (if applicable) | Serum β -HCG testing | Screening/baseline, every 4 weeks up to week 72 (EOT), unscheduled |

8.3.2 Cardiac Assessments

8.3.2.1 Electrocardiogram (ECG)

After the subject has rested approximately 10 minutes in a semi-supine position, standard 12-lead ECGs must be obtained in triplicate with a recommended minimal interval of 5 minutes between each ECG at the time points specified in Table 8-1, and Table 8-5. In this case recording of ECGs should be planned according to the true time of blood sample [REDACTED] rather than to the scheduled time point.

A standard 12 lead ECG will be performed:

- For Cohort A, B and C at screening and/or baseline, Week 1 day 1, Week 2 Day1, Week 4 Day 1, Week 12 Day 1, Week 24 Day 1, Week 36 Day 1, Week 48 Day 1, Week 60 Day 1, Week 72 Day 1 (end of study).
- Cohort C will require additional Week 8 Day 1 ECG in addition to the schedules mentioned above.

Table 8-2 ECG collection plan

| Week (or Cycle) | Time | ECG Type | Number of ECGs (per Visit) |
|---|---|----------|----------------------------|
| Screening/Baseline Day -21 to -1 / (all patients) | 3 serial ECGs at the screening visit | 12 Lead | 3 |
| Week 1 Day 1 | 3 serial ECGs at 2 h post dose | 12 Lead | 3 |
| Week 2 Day 1 | 3 serial ECGs pre-dose and at 2, 3, 4 h post dose | 12 Lead | 12 |

| Week (or Cycle) | Time | ECG Type | Number of ECGs (per Visit) |
|---|--------------------------------|----------|----------------------------|
| Week 4 Day 1 | 3 serial ECGs pre-dose | 12 Lead | 3 |
| Week 8 Day 1* | 3 serial ECGs pre-dose | 12 Lead | 3 |
| Week 12 Day 1 | 3 serial ECGs pre-dose | 12 Lead | 3 |
| Week 24 Day 1 | 3 serial ECGs pre-dose | 12 Lead | 3 |
| Week 36 Day 1 | 3 serial ECGs pre-dose | 12 Lead | 3 |
| Week 48 Day 1 | 3 serial ECGs pre-dose | 12 Lead | 3 |
| Week 60 Day 1 ⁺ | 3 serial ECGs pre-dose | 12 Lead | 3 |
| Week 72 Day (end of study) 1 | 3 serial ECGs 30 min post-dose | 12 Lead | 3 |
| Unscheduled or Unplanned sample | 3 serial ECGs | 12 Lead | 3 |
| 30 min +/- 5min allowed * Week 8 day 1 assessment is only applicable to Cohort C and in-person visit + only applicable to in-person visit | | | |

All ECGs performed will be independently reviewed. Instructions for the collection and transmission of these ECGs to the independent central reader will be provided in the [CABL001AUS04 ECG Manual].

Three serial ECGs (triplicate) should be performed ½ hour prior to dosing for pre-dose assessment. The serial ECGs should be taken approximately 5 minutes apart. All 3 ECGs for each time point should be sent to central ECG reader. Readings for QTc prolongation will be based on the average seen in the scans for each time point. The enrollment of patients has to be based on centrally assessed QTcF time. If one of the 3 serial ECGs prior to dosing on day 1 shows a QTcF \geq 450 msec (male) or \geq 460 msec (female) by automated reading, an immediate manual central reading must be requested by either contacting the medical monitor or by calling central ECG reader. The patient may not be dosed if the average of the manually read ECGs confirms a QTcF \geq 450 msec (male) or \geq 460 msec (female).

Dose adjustments in case of QT prolongation should be performed per [Section 6.5.2.1](#)

Additional unscheduled ECGs may be repeated at the discretion of the investigator at any time during the study as clinically indicated. Unscheduled ECGs with clinically significant findings should be collected in triplicate. Local cardiologist ECG assessment may also be performed at any time during the study at the discretion of the investigator.

All ECGs, including unscheduled triplicate safety ECGs with clinically relevant findings, collected during the study should be transmitted to the central core ECG laboratory for review.

The results of the centrally assessed ECGs are automatically transferred into the clinical database.

Clinically significant ECG abnormalities present at screening should be reported on the Medical History eCRF page. New or worsened clinically significant findings occurring after informed consent must be recorded on the Adverse Events eCRF page.

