5.2 Exclusion criteria

Patients eligible for this study must not meet any of the following criteria:

1. Known second chronic phase of CML after previous progression to AP/BC
2. Previous treatment with a hematopoietic stem-cell transplantation
3. Cardiac or cardiac repolarization abnormality, including any of the following:
 - History within 6 months prior to starting study treatment of myocardial infarction (MI), angina pectoris, coronary artery bypass graft (CABG)
 - Clinically significant cardiac arrhythmias (e.g., ventricular tachycardia), complete left bundle branch block, high-grade AV block (e.g., bifascicular block, Mobitz type II and third degree AV block)
 - QTcF at screening ≥ 450 msec (male patients), ≥ 460 msec (female patients)

- Long QT syndrome, family history of idiopathic sudden death or congenital long QT syndrome, or any of the following:
 - Risk factors for Torsades de Pointes (TdP) including uncorrected hypokalemia or hypomagnesemia, history of cardiac failure, or history of clinically significant/symptomatic bradycardia
 - Concomitant medication(s) with a “Known risk of Torsades de Pointes” per www.crediblemeds.org/ that cannot be discontinued or replaced 7 days prior to starting study drug by safe alternative medication.
 - Inability to determine the QTcF interval
- 4. Severe and/or uncontrolled concurrent medical disease that in the opinion of the investigator could cause unacceptable safety risks or compromise compliance with the protocol (e.g. uncontrolled diabetes, active or uncontrolled infection, pulmonary hypertension)
- 5. History of acute pancreatitis within 1 year of study entry or past medical history of chronic pancreatitis
- 6. Known presence of significant congenital or acquired bleeding disorder unrelated to cancer
- 7. History of other active malignancy within 3 years prior to study entry with the exception of previous or concomitant basal cell skin cancer and previous carcinoma in situ treated curatively
- 8. Impairment of gastrointestinal (GI) function or GI disease that may significantly alter the absorption of study drug (e.g. ulcerative disease, uncontrolled nausea, vomiting, diarrhea, malabsorption syndrome, small bowel resection, or gastric bypass surgery)
- 9. Previous treatment with or known/ suspected hypersensitivity to asciminib or any of its excipients.

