6.5.2.1 Dose adjustments for QTcF prolongation

If QTcF >500 msec or QTcF prolongation >60 msec from baseline is observed at any point during study treatment, and confirmed, the below guidance must be followed:

1. Assess the quality of the ECG recording and the QT value and repeat if needed
2. Interrupt study treatment until confirmed resolution of QTcF and as per dose reduction guidelines for non-hematological AEs.
3. Determine the serum electrolyte levels (in particular hypokalemia and hypomagnesemia). If abnormal, correct abnormalities before resuming study treatment.
4. Review concomitant medication associated with QT prolongation, including drugs with a “Known”, “Possible”, or “Conditional risk of Torsades de Pointes” (refer to www.crediblemeds.org/), and drugs with the potential to increase the risk of study drug exposure related QT prolongation.
5. Check the dosing schedule and treatment compliance

After confirming ECG reading at site, if QTcF > 500 msec

- Interrupt study treatment
- Repeat ECG and confirm ECG diagnosis by a cardiologist or central ECG lab
- If QTcF confirmed > 500 msec:
 - Correct electrolytes, eliminate culprit concomitant treatments, and identify clinical conditions that could potentially prolong the QT as per the ECG and QTc Clinical Safety Standards Guidelines
 - Consult with a cardiologist (or qualified specialist)
 - Increase cardiac monitoring as indicated, until the QTcF returns to ≤ 480 msec
- After resolution to ≤ 480 msec, consider re-introducing treatment at reduced dose, and increase ECG monitoring (e.g., pre dose and 2 hours post dose after one week and two weeks of treatment re-introduction)
- If QTcF remains ≤ 500 msec after dose reduction, continue planned ECG monitoring during subsequent treatment
- If QTcF recurs > 500 msec after dose reduction, discontinue subject from trial

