8.2 Participant demographics/other baseline characteristics

Patient demographics and baseline characteristics collected will include the following: date of birth, gender (and child bearing potential for female), race and ethnicity, height, weight, all relevant medical history including cardiovascular disease history, CML disease history,

including mutation status, and prior and concomitant medication including prior TKI therapy and antineoplastic medication.

Physical examination including extramedullary involvement, performance status, vital signs, ECGs, and laboratory assessments will be performed at screening.

Significant findings that were present prior to the signing of informed consent must be included in the Relevant Medical History/Current Medical Conditions page on the subject's eCRF. Significant new findings that begin or worsen after informed consent must be recorded on the AE page of the patient's eCRF.

The central reading of the screening ECGs as well as the results of the RQ-PCR must be available prior to the first dose of study treatment to evaluate eligibility and to stratify the patient.

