| Height and weight | 
Height in centimeters (cm) will be measured at screening only. Body weight (to the nearest 0.2 pounds [lb] in indoor clothing, but without shoes) will be measured at screening and at subsequent time points as specified in Table 8-1:
 
 • Screening • Week 1 Day 1 
With the exception of Weeks 12, 24, 36, 48 and 72, Height and Weight can be omitted for the remainder of the protocol
 |

Performance status:

ECOG Performance status scale ([Table 8-5](#)) will be used as described in the [Table 8-1](#):

- Screening
- Week 1 Day 1
- Every 4 weeks from Week 4 to Week 72 (End of treatment) or early discontinuation in case of premature discontinuation.
- More frequent examinations may be performed at the investigator’s discretion, if medically indicated.

ECOG Performance status scale will be used as described in [Table 8-5](#).

Table 8-5 Table ECOG Performance Status Scale

| Description | Grade |
|---|-------|
| Fully active, able to carry on all pre-disease activities without restriction. | 0 |
| Restricted in physically strenuous activity but ambulatory and able to carry out work of a light or sedentary nature e.g. light housework, office work. | 1 |
| Ambulatory and capable of all self-care but unable to carry out any work activities. Up and about more than 50% of waking hours. | 2 |
| Capable of only limited self-care, confined to bed or chair more than 50% of waking hours. | 3 |
| Completely disabled. Cannot carry on any self-care. Totally confined to bed or chair. | 4 |
| Dead. | 5 |

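### Protocol 8.3.2.1 can bar the first dose on a pre-dose Day 1 ECG triplicate, but Table 8-2 schedules only a 2 h post-dose triplicate that day

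*Protocol*

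**What the plan says.** Protocol 8.3.2.1 first asks for pre-dose triplicates to be taken half an hour before dosing, and says enrollment must rest on the centrally assessed QTcF. The rule at issue follows: "If one of the 3 serial ECGs prior to dosing on day 1 shows a QTcF" at or above 450 msec for men or 460 msec for women on automated reading, an urgent manual central reading must be obtained. The patient may not receive the dose if the manually read average confirms the value.

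Table 8-2 (ECG collection plan), in the same section, has these rows up to Week 2:

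- Screening/Baseline, Day -21 to -1: one triplicate at the screening visit, count 3.
- Week 1 Day 1: "3 serial ECGs at 2 h post dose", count 3.
- Week 2 Day 1: "3 serial ECGs pre-dose and at 2, 3, 4 h post dose", count 12.

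The opening of 8.3.2.1 tells sites to record ECGs "at the time points specified in Table 8-1, and Table 8-5". Table 8-1 marks an ECG at Week 1 Day 1 without a time relative to dose. The other table cited is headed "Table 8-5 Table ECOG Performance Status Scale" and has nothing to do with ECGs.

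Protocol 5.2 (exclusion 3) applies the same two QTcF limits at screening. Protocol 8.2 adds: "The central reading of the screening ECGs as well as the results of the RQ-PCR must be available prior to the first dose". SAP 2.1.1 defines the ECG baseline as the last assessment available before the date and time treatment starts.

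**The concern.** The stop rule depends on a measurement that the schedule does not contain. The only Day 1 triplicate in Table 8-2 comes two hours after the dose, too late to decide whether to give it. A site that reads the text closely may take a pre-dose set anyway. A site that works from the table will not.

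Two things are at stake:

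- **Safety.** A QTcF that was acceptable at screening but has reached the limit by Day 1 would go unseen until after the first dose. The protocol itself allows QT-relevant conditions to change in that interval. Drugs with a known torsades risk may be stopped or replaced up to 7 days before start (5.2), and low potassium, magnesium or calcium may be corrected before the first dose (8.1).
- **Baseline.** Under the SAP definition, a site following the table supplies a screening baseline up to 21 days old, while a site following the text supplies a Day 1 baseline. The change-from-baseline ECG summaries would then mix the two. The choice also bears on Protocol 6.5.2.1, which interrupts treatment for "QTcF prolongation >60 msec from baseline" without saying which tracing is the baseline.

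QT is not a side issue in this trial. Protocol 1.1.2.2 reports two new values above 500 msec on asciminib monotherapy, one of them at 80 mg QD, the Cohort B regimen. QTc prolongation is on the SAP 5.4 list of events of special interest. Notable ECG abnormalities are among the primary analysis variables (Protocol 12.4, SAP 2.5).

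**Working it through.** **1. Is the Week 1 Day 1 row shorthand that includes a pre-dose set?** Table 8-2 states a count per visit, which can be checked as time points × 3 replicates.

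| Visit | Time points listed | × 3 | Stated count |
|---|---|---|---|
| Screening | 1 | 3 | 3 |
| Week 1 Day 1 | 1 (2 h post dose) | 3 | 3 |
| Week 2 Day 1 | 4 (pre-dose, 2, 3, 4 h) | 12 | 12 |
| Week 4 Day 1 | 1 (pre-dose) | 3 | 3 |
| Week 72 | 1 | 3 | 3 |

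Every count reproduces. The post-dose triplicate uses up the three tracings of Week 1 Day 1. The Week 2 row shows that the table names and counts a pre-dose set where one is planned. With the set that the stop rule needs, Week 1 Day 1 would be 2 × 3 = 6.

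**2. Does another table supply the time?** No. Table 8-1 gives no time relative to dose, and Table 8-5 is the performance-status scale. The only scheduled ECG before the first dose is the screening triplicate.

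**3. How often might a patient cross the limit between screening and Day 1?** The documents give neither a rate nor a QTcF variance, so this is an assumption shown over a range. Take the triplicate-mean QTcF on each day as normal with between-day SD *s*, independent between days, with the same true mean. For a patient screened *d* ms below the limit:

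P(at or above the limit on Day 1) = 1 − Φ( d / (s√2) )

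| d | s = 6 ms | s = 8 ms | s = 12 ms |
|---|---|---|---|
| 10 ms | 0.119 | 0.188 | 0.278 |
| 20 ms | 0.009 | 0.039 | 0.119 |

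This applies only to patients near the limit, and the documents do not say how many of the 115 those would be.

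**4. Burden of adding the pre-dose set** (Table 8-2, all visits in person):

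- Cohorts A and B: nine visits × 3 + 12 at Week 2 = 39 tracings per patient.
- Cohort C: 39 + 3 at Week 8 = 42.
- Scheduled total: 90 × 39 + 25 × 42 = 3,510 + 1,050 = 4,560.
- Added: 115 × 3 = 345, and 345 / 4,560 = 7.6%.

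**The case against.** The strongest reply is that the protocol text already contains the requirement. It asks for triplicates half an hour before dosing and states the Day 1 rule in mandatory terms, so only a table row lags behind. That is fair as far as it goes, and a careful site could comply. But sites plan visits from the collection table, and this table is explicit about both time and count.

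A second reply is that the ECGs before Day 1 dosing may simply mean the screening triplicate. The limits are the same, the preceding sentence concerns enrollment, and Table 8-2 labels that visit Screening/Baseline. On this reading nothing conflicts. It fits poorly, though, with a rule that names Day 1, demands an urgent reading and withholds the dose, and screening already has its own gate in 5.2 and 8.2. If it is what the sponsor meant, the sentence still needs rewording.

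Several limits on the size of the problem do stand:

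- The ECG Manual cited in 8.3.2.1 is not available here and may give sites the Day 1 timing.
- Residual risk is reduced by electrolyte correction before the first dose, withdrawal of known-risk drugs, the 2 h Day 1 triplicate (within the 2 to 3 h Tmax range), the 12 tracings at Week 2, and unscheduled ECGs.
- A screening baseline satisfies the SAP definition. The SAP's notable QTcF categories use absolute cut-offs (above 480 and above 500 ms), so the baseline effect falls mainly on descriptive change summaries, with no testing.
- The crossing probabilities describe day-to-day noise under no true change. They also centre the true mean on the screening value. For a patient near an upper limit this ignores regression to the mean and probably overstates the chance.

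**Conclusion.** The inconsistency is real and sits in current, legible text: the first-dose stop rule cannot be carried out from the ECG schedule as written. It should be corrected. It is not an entry-safety failure, because the screening exclusion uses the same limits and must be centrally read before dosing. The gap is confined to patients whose QTcF reaches the limit in the up to 21 days after screening, and to a QTcF baseline that may come from different visits at different sites.

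The illustrative crossing chance of 12% to 28% at 10 ms below the limit, and 1% to 12% at 20 ms below, rests on the assumed SD of 6 to 12 ms and is probably on the high side. The mismatch itself does not depend on those figures. Sample size and the adverse-event analysis are unaffected.

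**What to change.** Change the Week 1 Day 1 row of Table 8-2 to three serial ECGs pre-dose and three at 2 h post dose, count 6. State that the pre-dose set serves both the dosing decision and the QTcF baseline, for the SAP summaries and for the 60 msec rule in 6.5.2.1. Correct the cross-reference in 8.3.2.1 from Table 8-5 to Table 8-2. If the screening triplicate was intended, reword the rule to say so and leave the row alone.

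The text change is small but is a protocol amendment, with the approvals that Protocol 14.1 requires. It adds three tracings per patient, at most 345 in total (7.6%), at a visit where ECGs are already taken. The increase is smaller to the extent that sites already take the pre-dose set on the strength of the text. First dosing may have to wait for a manual central reading when an automated value is at or above the limit. For patients dosed before the change (25 had been enrolled at Amendment 3), the report can state whether each QTcF baseline came from screening or from Day 1.

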8.3.2.2 Echocardiogram

Echocardiograms will be performed to monitor cardiac safety. Assessments are scheduled at screening/baseline, and if clinically indicated at Week 20 and end of treatment visits. Echocardiogram is the only acceptable assessment for cardiac safety. The echocardiogram will be performed at the discretion of the treating physician locally if he/she recommends assessing the left ventricular ejection fraction due to potential concerns for cardiac safety. Any clinically significant findings will be collected and reported in the database (i.e. reported as adverse events).

